3.3. Inclusion of Women and Minorities

Both men and women of all races and ethnic groups are eligible for this trial.

4. Site Enrollment Requirements

Site must submit all required essential documents including:

- IRB/Regulatory Approval of protocol, informed consent document and study participant materials obtained in one of two ways:
 - Option 1: use the Alliance Foundation Trials (AFT) Central IRB as the study site's IRB of record for this study [AFT will be using Quorum as the CIRB vendor for this study] **-OR-**

- Option 2: Submit protocol to site institutional IRB
- Site Principal Investigator FDA Form 1572 and Curriculum Vitae
- Medical License
- Investigator's Protocol Signature Page
- Documentation of ICH Good Clinical Practice (ICH/GCP)
- Investigator Brochure Acknowledgement(s)

Essential documents must be submitted to the AFT electronic Trial Master File, accessible via the AFT website, [REDACTED] Sites will receive site selection correspondence with detailed requirements for site activation.

5. Patient Enrollment

Informed consent: The patient must be aware of the neoplastic nature of his/her disease and willingly consent after being informed of the procedure to be followed, the experimental nature of the therapy, alternatives, potential benefits, side-effects, risks, and discomforts. Current human protection committee approval of this protocol and a consent form is required prior to patient consent and enrollment.

Patients with impaired decision-making capacity may be enrolled on this study, where institutional policy and IRB of record allow.

Patient enrollment will be facilitated using the RAVE EDC system.

Patient must be enrolled prior to submission of biospecimens. Prior to accessing EDC, site staff should verify the following:

- All eligibility criteria have been met within the protocol stated timeframes.
- All patients have signed an appropriate consent from and HIPAA authorization form

The RAVE-EDC system will provide the site with a confirmation of enrollment and treatment information. Please retain this confirmation for your records.

After written informed consent has been obtained, the study site will obtain a unique patient identifier by entering the patient into the patient enrollment system. The patient identifier will stay the same throughout the entire study. Patients must receive this identifier prior to submission of biospecimens.

6. Treatment Plan

6.1. Treatment Regimen

At the time of registration, the dose level of Ibrutinib and Lenalidomide will be assigned to the patient. The dose levels being examined in this study are presented in the following table:

Table 7 Dose levels for Ibrutinib, Lenalidomide and Dexamethasone

Dose Level	Ibrutinib	Lenalidomide	Dexamethasone ^a
1 (starting dose)	560 mg	15 mg	40mg

2	560mg	25 mg	40mg
3	840mg	25 mg	40mg

a The starting dose of dexamethasone will be reduced to 20 mg based on tolerability or if the patient is 75 years or older at the time of registration.

Table 8 Treatment Plan

Agent	Dose	Route	Days	ReRx
Ibrutinib	assigned at time of registration	Oral	1-28	
Lenalidomide	assigned at time of registration	Oral	1-21	
Dexamethasone	40 mg if age < 75 years old at registration	Oral	1, 8, 15, 22	Every 28 days
	20 mg if age ≥ 75 years old at registration			

Treatment days are based on 28-day cycles. Patients will be treated on an outpatient basis. Refer to Protocol Section 11.0 for expected toxicities of study agents.

Please refer to Section 6.1 for dose escalation guidelines for ibrutinib.

6.2. Pre-Treatment Criteria

A treatment may begin on the scheduled Day 1 of a new cycle if:

- The ANC is $\geq 1,000/\mu\text{L}$;
- The platelet count is $\geq 50,000/\mu\text{L}$;
- Any Ibrutinib or lenalidomide-related allergic reaction/hypersensitivity or sinus bradycardia/ other cardiac arrhythmia adverse event that may have occurred has resolved to \leq grade 1 severity;
- Any other Ibrutinib or lenalidomide-related adverse event that may have occurred has resolved to \leq grade 2 severity.

Laboratory values (excluding Child Pugh score) on Cycle 1, Day 1 must meet eligibility criteria per Section 3.1 (Inclusion Criteria).

6.2.1 Cycle 1 Day 1

Cycle 1 Day 1 hematology and chemistry laboratory assessments will be repeated if not performed within 7 days of starting study treatment.

6.2.2 Subsequent Cycles

Refer to dose modifications sections (Section 7) for re-treatment criteria on Day 1 of subsequent cycles.

6.3. Agent Administration

6.3.1 Ibrutinib

Ibrutinib is administered orally once daily. The capsules are to be taken around the same time each day with 8 ounces (approximately 240 mL) of water. The capsules should be swallowed intact and subjects should not attempt to open capsules or dissolve them in water. The use of strong CYP3A inhibitors/inducers, and grapefruit and Seville oranges should be avoided for the duration of the study.

If a dose is not taken at the scheduled time, it can be taken as soon as possible on the same day with a return to the normal schedule the following day. The patient should not take extra capsules to make up the missed dose.

The first dose of ibrutinib will be delivered in the clinic on Day 1, after which subsequent dosing is typically on an outpatient basis. Ibrutinib will be dispensed to subjects in bottles at each visit. Study drug may not be shipped to the subject without approval from PCYC and may not be dispensed to anyone other than the subject. Unused ibrutinib dispensed during previous visits must be returned to the site and drug accountability records updated at each visit. Returned capsules must not be redispensed to anyone.

6.3.1.1 Overdose

There is no specific experience in the management of ibrutinib overdose in patients. No maximum tolerated dose (MTD) was reached in the Phase 1 study in which subjects received up to 12.5 mg/kg/day (1400 mg/day). Healthy subjects were exposed up to single dose of 1680 mg. One healthy subject experienced reversible Grade 4 hepatic enzyme increases (AST and ALT) after a dose of 1680 mg. Subjects who ingested more than the recommended dosage should be closely monitored and given appropriate supportive treatment.

Refer to Section 11 for further information regarding AE reporting.

6.3.2 Lenalidomide

Lenalidomide is a commercially available agent that is FDA approved for this indication. Administration of lenalidomide may be per package insert, institutional standard, or investigator discretion.

6.3.3 Dexamethasone

Dexamethasone is a commercially available agent that is FDA approved for this indication. Administration of dexamethasone may be per package insert, institutional standard, or investigator discretion.

6.3.4 Compliance

Patients should be instructed to record daily administration of the study drugs in a drug or medication diary.

6.4. Supportive Care and Concomitant Medications

6.4.1 Permitted Concomitant Medications

- **Anti-diarrheal medications:** Diarrhea can be managed conservatively with loperamide. The recommended dose of loperamide is 4 mg at first onset, followed by 2 mg every 2-4 hours until diarrhea free (maximum 16 mg/day).
 - In the event of grade 3 or 4 diarrhea, the following supportive measures are allowed: hydration, octreotide, and antidiarrheals.
 - If diarrhea is severe (requiring intravenous rehydration) and/or associated fever or severe neutropenia (grade 3 or 4), broad-spectrum antibiotics must be prescribed. Patients with severe diarrhea or any diarrhea associated with severe nausea or vomiting should be hospitalized for intravenous hydration and correction of electrolyte imbalances.
- Transfusions of blood products may be given in accordance with institutional policy.
- DVT prophylaxis: patients will be required to be on some form of anticoagulation with at least aspirin 81 mg daily while on lenalidomide.
- Low dose oral corticosteroid of short courses (≤ 14 days) of treatment for non-cancer related medical reasons (e.g. joint inflammation, asthma exacerbation, rash, antiemetic use and infusion reactions) at doses that do not exceed 10 mg per day of prednisone or equivalent are permitted.
- Usage of antimicrobial prophylaxis in accordance with standard practice (eg, ASCO guidelines [Flower 2013]) is permitted and should be considered in subjects who are at increased risk for opportunistic infections.
- Corticosteroid for treatment of autoimmune cytopenias for < 14 days at doses that do not exceed 100 mg per day of prednisone or equivalent are permitted.
- Localized palliative radiation therapy may be given for pain control. This will however need to be approved by study chairs. In addition, if there is any other situation in which radiation is required in the course of study therapy for an event that does not constitute disease progression, radiation may be administered as long as lenalidomide and ibrutinib are restarted immediately following radiation therapy.
- Neutrophil growth factors:
 - The use of filgrastim and pegfilgrastim or red blood cell growth factors (erythropoietin) is permitted per institutional policy and in accordance with the ASCO guidelines (Smith 2006). Neutrophil growth factors are not allowed during cycle 1 in the course of DLT assessment.

6.4.2 Medications to be Used with Caution

6.4.2.1 CYP3A – Inhibitors/Inducers

Ibrutinib is metabolized primarily by CYP3A4. Concomitant use of ibrutinib and drugs that strongly or moderately inhibit CYP3A can increase ibrutinib exposure and therefore strong

CYP3A inhibitors should be avoided.

- If a strong CYP3A inhibitor (eg, ketoconazole, indinavir, nelfinavir, ritonavir, saquinavir, clarithromycin, telithromycin, itraconazole, nefazadone, cobicistat and posaconazole) must be used, reduce ibrutinib dose to 140 mg for the duration of the inhibitor use or withhold ibrutinib treatment temporarily (for 7 days or less). Subjects should be monitored for signs of ibrutinib toxicity.
- If a moderate CYP3A inhibitor (eg, voriconazole, erythromycin, amprenavir, aprepitant, atazanavir, ciprofloxacin, crizotinib, diltiazem, fluconazole, fosamprenavir, imatinib, verapamil, amiodarone, and dronedarone) is indicated, reduce ibrutinib to 140 mg for the duration of the inhibitor use.
- Avoid grapefruit and Seville oranges during ibrutinib treatment, as these contain moderate inhibitors of CYP3A (see Section 6.3.1).
- No dose adjustment is required in combination with mild inhibitors.
- Avoid concomitant use of systemic strong CYP3A inducers (eg. Carbamazepine, rifampin, phenytoin, and St. John's Wort). Consider alternative agents with less CYP3A induction.

A list of common CYP3A inhibitors and inducers is provided in Appendix II. A comprehensive list of inhibitors, inducers and substrates may be found at <http://medicine.iupui.edu/clinpharm/ddis/main-table/>.

This website is continually revised and should be checked frequently for updates.

For the most comprehensive effect of CYP3A inhibitors or inducers of ibrutinib exposure, please refer to the current version of the IB.

6.4.2.2 Drugs That May Have Their Plasma Concentrations Altered by Ibrutinib

In vitro studies indicated that ibrutinib is not a substrate of P-glycoprotein (P-gp), but is a mild inhibitor. Ibrutinib is not expected to have systemic drug-drug interactions with P-gp substrates. However, it cannot be excluded that ibrutinib could inhibit intestinal P-gp after a therapeutic dose. There is no clinical data available; therefore, to avoid a potential interaction in the GI tract, narrow therapeutic range P-gp substrates such as digoxin, should be taken at least 6 hours before or after ibrutinib.

6.4.2.3 Antiplatelet Agents and Anticoagulants

Use ibrutinib with caution in subjects requiring other anticoagulants or medications that inhibit platelet function. In an in vitro platelet function study, inhibitory effects of ibrutinib on collagen-induced platelet aggregation were observed. Supplements such as fish oil and vitamin E preparations should be avoided during treatment with ibrutinib. Bleeding events of any grade, including bruising and petechiae, occurred in subjects with ibrutinib. Subjects with congenital bleeding diathesis have not been studied. Ibrutinib should be held at least 3 to 7 days pre- and post-surgery depending on the type of surgery and the risk of bleeding.

Subjects requiring the initiation of therapeutic anticoagulation therapy (eg, atrial fibrillation) should be monitored closely for signs and symptoms of bleeding and the risks and benefits of

continuing ibrutinib treatment.

6.4.3 Prohibited Concomitant Medications

Any non-study protocol related chemotherapy, anticancer immunotherapy, experimental therapy are prohibited while the subject is receiving protocol treatment. Radiation given for palliation of pain is allowed and is not considered protocol therapy violation. However, approval should be given by the chairpersons of the study.

Erythropoietic growth factors (eg, erythropoietin and darbepoetin) and neutrophil growth factors (eg, filgrastim and peg-filgrastim) are also prohibited during initial treatment, DLT assessment period.

Warfarin or vitamin K antagonists should not be administered concomitantly with ibrutinib.

6.4.4 Guidelines for Ibrutinib Management with Surgeries or Procedure

Ibrutinib may increase risk of bleeding with invasive procedures or surgery. The following guidance should be applied to the use of ibrutinib in the perioperative period for subjects who require surgical intervention or an invasive procedure while receiving ibrutinib.

6.4.4.1 Minor Surgical Procedures

For minor procedures (such as a central line placement, skin or needle biopsy, lumbar puncture [other than shunt reservoir access], thoracentesis, or paracentesis) ibrutinib should be held for at least 3 days prior to the procedure and should not be restarted for at least 3 days after the procedure. For bone marrow biopsies that are performed while the subject is on ibrutinib, it is not necessary to hold ibrutinib for these procedures.

6.4.4.2 Major Surgical Procedures

For any surgery or invasive procedure requiring sutures or staples for closure, ibrutinib should be held at least 7 days prior to the intervention (except for emergency procedures) and should be held at least 7 days after the procedure and restarted at the discretion of the investigator when the surgical site is reasonably healed without serosanguineous drainage or the need for drainage tubes.

7. Dose De-Escalation

7.1. Definition of Dose-Limiting Toxicity (DLT)

Attributions should be made as possibly, probably, or definite.

Table 9 Dose limiting toxicities (DLT)

Toxicity	DLT Definition
Hematologic	Grade 4 thrombocytopenia or Grade 3 thrombocytopenia with bleeding or requirement for platelet transfusion.

	Grade 4 neutropenia lasting more than 5 days.
Other nonhematologic*	≥ grade 3 as per NCI Common Terminology Criteria for Adverse Events (CTCAE) version 5.0*
	Grade 4 febrile neutropenia
	≥ grade 3 hyperglycemia due to dexamethasone if it cannot be controlled with appropriate therapy
	Treatment delays ≥ 21 days for any non-hematologic or hematological toxicity
	Treatment related death
	Grade ≥ 3 thrombotic/embolic events including DVT
	Grade 4 nausea, vomiting and diarrhea

*except grade 3 nausea, vomiting, diarrhea that does not require tube feeding, total parenteral nutrition or prolonged hospitalization, diarrhea responsive to medical treatment, nausea or vomiting controlled with antiemetics, or transient electrolyte abnormalities that resolve < grade 1 within 48 hours

7.2. Determination of Maximum Tolerated Dose (MTD)

The maximum tolerated dose is defined as the highest dose level among those tested where at most one out of 6 patients develops a DLT prior to the start of their second cycle of treatment and the next highest dose level is such that 2 out of a maximum of 6 patients treated at this dose level developed a DLT prior to the start of their second cycle of treatment.

7.3. Enrollment and determination of MTD

A minimum of 2 or a maximum of 6 patients will be accrued to a given dose level. Enrollment will begin with 3 patients accrued to dose level 1.

Dose de/escalation scheme for Dose 1:

- If none of the first 3 patients treated at dose level 1 develops a DLT during the first cycle of treatment, then the next cohort of 3 patients will be enrolled at dose level 2.
- If one of the first 3 patients treated at dose level 1 develops a DLT during the first cycle of treatment, then an additional cohort of 3 patients will be enrolled at the current dose level.
- If at most 1 of the 6 patients enrolled at dose level 1 develops a DLT during the first cycle of treatment, the next cohort of 3 patients will be treated at dose level 2.
- If 2 or more of the 6 patients enrolled at level 1 develops a DLT during the first cycle of treatment, enrollment will be halted, and the study team will discuss whether to

submit an amendment to reopen enrollment to a lower dose level.-

As of October 7, 2021, 3 patients have been enrolled onto dose level 2.

Dose de/escalation scheme for Dose 2:

- If none of the first 3 patients treated at dose level 2 develops a DLT during the first cycle of treatment, then the next cohort of 3 patients will be enrolled onto dose level 3.
- If one of the 3 patients treated at dose level 2 develops a DLT during the first cycle of treatment, then the next cohort of 3 patients will be enrolled at dose level 2.
 - If 2 or more of the 6 patients treated at dose level 2 develops a DLT then an additional 10 patients will be enrolled onto dose level 1 before completing enrollment.
- If 2 or more of 3 patients treated at dose level 2 develops a DLT during the first cycle of treatment, an additional 10 patients will be enrolled onto dose level 1 to further assess safety before completing enrollment.

Dose de/escalation scheme for Dose 3 (if applicable):

- If at most 1 of 6 patients treated at dose level 2 develops a DLT during the first cycle of treatment and 1 or fewer of the 6 patients treated at dose level 3 develops a DLT in the first cycle of treatment, then an additional 4 patients will be treated on dose level 3 before completing enrollment.
- If at most 1 of 6 patients treated at dose level 2 develops a DLT during the first cycle of treatment and 2 or more of the 3-6 patients treated at dose level 3 develops a DLT during the first cycle of treatment, then an additional 7 patients will be enrolled onto dose level 2 before completing enrollment.
- If at most 1 of 6 patients treated at dose level 3 develops a DLT during the first cycle of treatment then an additional 4 patients will be enrolled onto dose level 3 before completing enrollment.
- If 2 or more of the 3-6 patients treated at dose level 3 develops a DLT during the first cycle of treatment then an additional 7 patients will be enrolled onto dose level 2 before completing enrollment.

8. Dose and Treatment Modifications

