Secondary Objectives	
To determine the following:
 
 1. Progression-free survival (PFS): Time from registration to disease progression or death due to any cause. 2. Overall survival (OS): Time from registration to death due to any cause. 3. Overall Response Rate: Time from start of treatment to objective response 4. Duration of response: Time from documented response to disease progression among those patients whose disease meets the IMWG criteria for disease response
Correlative Science Objectives	To perform select immunologic studies with this combination therapy.
Study Design	
Part 1: Dose Escalation
 
Patients in the dose escalation phase will receive oral treatment with:
 
Ibrutinib: Days 1-28 of every 28-day cycle Lenalidomide: Days 1-21 of every 28-day cycle Dexamethasone: 40 mg for patients <75 at the time of registration 20 mg for patients ≥ 75 at registration on Days 1, 8, 15 and 22 of every Cycle. One cycle is 28 days.
 
Starting doses of ibrutinib and lenalidomide will be assigned at the time of registration. A minimum of 2 or a maximum of 6 patients will be accrued to a given dose level. Doses will not be escalated in any individual patient. If none of the first 3 patients treated at a given dose level develops a DLT during the first cycle of treatment, enrollment to the dose level will be closed and enrollment will reopen at next higher dose level. If there are no other higher dose levels to be tested, three additional patients will be enrolled at the current dose level to confirm MTD. If one of the first 3 patients treated at a given dose level develops a DLT during the first cycle of treatment, three additional patients will be enrolled onto the current dose level. If, at any time in the enrollment of these 3 additional patients, a patient develops a DLT, enrollment will be closed to this dose level. Enrollment will be reopened to the next lower dose level if fewer than 6 patients have been treated at that dose level. If none of these 3 additional patients develops a DLT during the first cycle of treatment, enrollment to this dose level will be closed and enrollment will reopen at next higher dose level. If

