The maximum tolerated dose is defined as the highest dose level among those tested where at most 1 out of 6 patients develops a DLT prior to the start of their second cycle of treatment and the next highest dose level is such that 2 or more out of a maximum of 6 patients treated at this dose level developed a DLT prior to the start of their second cycle of treatment.

Enrollment and determination of MTD

A minimum of 2 or a maximum of 6 patients will be accrued to a given dose level. Doses will not be escalated in any individual patient. If none of the first 3 patients treated at a given dose level develops a DLT during the first cycle of treatment, enrollment to the dose level will be closed and enrollment will reopen at next higher dose level. If there are no other higher dose levels to be tested, three additional patients will be enrolled at the current dose level to confirm MTD. If one of the first 3 patients treated at a given dose level develops a DLT during the first cycle of treatment, three additional patients will enroll onto the current dose level. If, at any time in the enrollment of these 3 additional patients, a patient develops a DLT, enrollment will be closed to this dose level. Enrollment will be re-opened to the next lower dose level if fewer than

6 patients have been treated at that dose level. If none of these 3 additional patients develops a DLT during the first cycle of treatment, enrollment to this dose level will be closed and enrollment will reopen at next higher dose level. If there are no other higher dose levels to be tested, this will be considered the MTD.

For this protocol, the patient must return to their registration institution for evaluation and continuation of treatment (at least every 28 ± 3 days) according to the test schedule. Patients who have not had disease progression and have experienced acceptable toxicity will be eligible to continue protocol retreatment at their current dose level until disease progression, unacceptable toxicity, or refusal. Those patients who have not progressed and who have experienced unacceptable toxicity may be eligible to continue protocol retreatment at a lower dose.

Criteria for discontinuation of all protocol therapy include:

- Tumor progression
- Request by the patient to withdraw
- Unacceptable adverse events
- Treatment delay of >4weeks

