8.2. Lenalidomide, ibrutinib, and dexamethasone dose delay modifications

If treatment is held for more than 28 days, then all study treatment will be discontinued

Table 13 Lenalidomide, ibrutinib, and dexamethasone dose delay modifications

Neutropenia	Grade 3 or greater on day 1 of cycle: hold lenalidomide and monitor CBC weekly; if resolves to \leq grade 2 within 4 weeks, resume lenalidomide with 5mg dose reduction. During treatment, G-CSF or GM-CSF may be used after completion of cycle 1 for neutropenia at the discretion of as needed by the treating physician.
Febrile Neutropenia	Hold lenalidomide for the remainder of the cycle. Following completion of cycle 1, consider G-CSF administration until there is adequate count recovery ANC \geq 1000/ μ L + absence of fever. If neutropenia resolves \leq grade 2, resume with lenalidomide at 5 mg dose reduction for subsequent cycles
Thrombocytopenia	If grade 3 or greater, hold lenalidomide the remainder of the cycle and until platelets \geq 50,000/ μ L. Then resume lenalidomide at 5 mg dose reduction for subsequent cycles Platelet transfusion may be given following completion of cycle 1. Platelet transfusion for severe thrombocytopenia may be administered in cycle 1 at investigator discretion following discussion with Principal Investigators.
Anemia	For grade 3 or greater, hold lenalidomide for the remainder of the cycle and until hemoglobin recovers to \leq grade 2. Red cell transfusion may be given.
Fatigue (asthenia, malaise)	For intolerable grade 2 or grade 3-4, hold protocol therapy thought to be probable or definitely related to the reaction until resolves to \leq grade 1, then resume protocol therapy with dose reduction of implicated protocol therapy by one dose level (5 mg for lenalidomide, 1 dose level below for Ibrutinib and/or 50% for dexamethasone).
Rash	If grade 3 hold lenalidomide and ibrutinib until resolves to \leq grade 2, then resume protocol therapy. Antihistamine (Benadryl, Claritin, zyrtec) may be given. If grade \geq 3 rash recurs, hold therapy until rash resolves to \leq grade 2, resume with one level dose reduction of agent(s) believed to be responsible for rash. For grade 4 rash, exfoliative or bullous rash, Stevens-Johnson Syndrome, toxic epidermal necrolysis, drug reaction with eosinophilia and systemic symptoms (DRESS), permanently discontinue lenalidomide

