14.3.2 Statement for Primary Endpoint

The primary endpoint of the dose escalation portion of this phase I study is the MTD. The maximum tolerated dose is defined as the highest dose level among those tested where at most one out of 6 patients develops a DLT prior to the start of their second cycle of treatment and the next highest dose level is such that 2 or more patients among the maximum of 6 patients treated at that dose level developed a DLT prior to the start of their second cycle of treatment.

The primary endpoint of the expansion portion of this phase I study is the objective response rate. The objective response rate is the percent of patients who meet the International Myeloma Working Group Response Criteria for sCR, CR, VGPR, or PR on two consecutive evaluations at least 4 weeks apart among the patients who began study treatment. A 90% binomial confidence interval will be constructed for the overall objective response rate.

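### Escalation rules count DLTs in the 28-day first cycle but the MTD counts them until cycle 2 starts, so a DLT by delayed cycle 2 can fall between the two

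*Combined protocol and SAP*

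**What the plan says.** The plan states the DLT window in three ways.

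- **Cycle 1 only.** The enrolment rules in the synopsis and Section 1.2 say "If none of the first 3 patients treated at a given dose level develops a DLT during the first cycle of treatment". Section 7.3 uses the same window for almost all its rules, starting with "If none of the first 3 patients treated at dose level 1 develops a DLT during the first cycle of treatment". The synopsis adds: "One cycle is 28 days".
- **Until cycle 2 starts.** Section 14.3.2, which defines the primary endpoint of the escalation part, requires that "at most one out of 6 patients develops a DLT prior to the start of their second cycle of treatment". Section 7.2 and the MTD paragraph of Section 1.2 use the same limit.
- **No window.** Section 14.1 restates the rules for dose levels 2 and 3 without a time limit. The MTD definition in Section 2.4.1 and the dose level 2 sub-bullet in Section 7.3 on two or more DLTs among six patients have none either.

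Table 9 in Section 7.1 lists as a DLT "Treatment delays ≥ 21 days for any non-hematologic or hematological toxicity". The start of a cycle depends on recovery. Section 6.2 opens its conditions, which include neutrophil and platelet minimums, with "A treatment may begin on the scheduled Day 1 of a new cycle if". For neutropenia, Table 13 in Section 8.2 says "Grade 3 or greater on day 1 of cycle: hold lenalidomide and monitor CBC weekly". Section 8.2 also says "If treatment is held for more than 28 days, then all study treatment will be discontinued", so a hold can pass 21 days while the patient is still on study treatment.

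No section says when a patient becomes evaluable for DLT, holds a cohort decision until every patient has started cycle 2, or says how to count a patient whose cycle 2 is pending.

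**The concern.** For a patient who starts cycle 2 on time, the first two windows are the same. They separate only when cycle 2 is late, which is a case that the delay criterion exists to catch. If the rule that opens the next level closes its count at day 28, a cohort can be declared clear while one of its patients is still on hold and may yet meet a listed DLT criterion.

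Two things are at stake. The next cohort could begin at a higher dose before the current one is resolved. And the level selected under Section 7.3 could fail the definition in Section 14.3.2, so that the trial's conduct and its primary endpoint rest on different counts of the same patients.

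**Working it through.** The plan gives no target DLT rate and no operating characteristics for its 3+3 rule, so there is no stated figure to reproduce. The check is a day count, followed by an illustration with assumed rates.

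**Day count.** Inputs: cycle length 28 days (synopsis) and delay criterion 21 days (Table 9).

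- Cycle 2 is due on day 28 + 1 = 29.
- A 21-day delay covers days 29 to 29 + 20 = 49. The earliest start after it is day 50, or days 47 to 53 if the ± 3 day visit window in Section 1.2 shifts the schedule.
- The delay is therefore complete 49 − 28 = 21 days after cycle 1 ends. That is outside the cycle 1 window but inside the MTD window, because cycle 2 has not begun.
- A hold within cycle 1 reaches 21 days by day 28 only if it starts by day 28 − 21 + 1 = 8.

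**Who is affected.** Many toxicities that would delay cycle 2 are already DLTs by grade. Table 9 does not list grade 3 neutropenia, or grade 3 thrombocytopenia without bleeding or transfusion, as hematologic DLTs, yet the minimum counts in Section 6.2 can keep such patients from starting cycle 2. For them, delay is the main or only route to a DLT.

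**Effect on a count.** A level cleared at 0/3 becomes 1/3 with one late DLT, which calls for three more patients instead of escalation. A level cleared at 1/6 becomes 2/6, which no longer meets the MTD definition.

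**Illustration (assumed rates, not in the documents).** Let p1 be the probability of a DLT within cycle 1, and q the probability of a delay DLT after day 28 among patients without one. The rate counted up to the start of cycle 2 is p = 1 − (1 − p1)(1 − q). A level below the top one is cleared at 0/3, or at 1/3 followed by 0/3:

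P(clear) = (1 − p)³ + 3p(1 − p)²(1 − p)³ = (1 − p)³ + 3p(1 − p)⁵

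| p1 | q | p | P(clear), cycle 1 only | P(clear), to start of cycle 2 |
|---|---|---|---|---|
| 0.20 | 0.05 | 0.240 | 0.709 | 0.622 |
| 0.20 | 0.10 | 0.280 | 0.709 | 0.536 |
| 0.20 | 0.15 | 0.320 | 0.709 | 0.454 |
| 0.10 | 0.05 | 0.145 | 0.906 | 0.824 |
| 0.10 | 0.10 | 0.190 | 0.906 | 0.730 |
| 0.10 | 0.15 | 0.235 | 0.906 | 0.632 |

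Worked example for p = 0.20: 0.8³ + 3(0.2)(0.8⁵) = 0.512 + 0.197 = 0.709. For p = 0.24: 0.76³ + 3(0.24)(0.76⁵) = 0.439 + 0.183 = 0.622.

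The chance that at least one of three patients without an in-cycle DLT later has a delay DLT is 1 − (1 − q)³ = 0.143, 0.271 or 0.386 for q = 0.05, 0.10 or 0.15.

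**The case against.** The best defence is that the first cycle can be understood to last until the second begins. Section 1.2 puts the MTD definition directly before the enrolment rules, and Section 7.2 directly precedes Section 7.3, so the authors may have meant one window. On that reading there is no conflict. It is a possible reading, but no section states it, and the fixed 28-day cycle points the other way. Sites could apply the rules differently.

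A reader might infer that a delay DLT can never count towards escalation, or that every rule is limited to cycle 1. The documents support neither. A hold that starts by day 8 can qualify within cycle 1, and Section 14.1 and one sub-bullet in Section 7.3 set no limit.

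The affected group is also narrow. Most non-hematologic events of grade 3 or higher, grade 4 thrombocytopenia and grade 4 neutropenia beyond 5 days are DLTs without any delay. Table 13 allows G-CSF after cycle 1, which should shorten neutropenic delays. Against that, neutrophil growth factors are barred in cycle 1 (Section 6.4.1), and Section 1.1.2.3 reports 38% grade 3-4 neutropenia with ibrutinib plus lenalidomide in mantle cell lymphoma, so slow count recovery is foreseeable.

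Section 14.2 expects each group of three to be enrolled and followed over 4-6 months, against about 50 days for a delay to be complete. That makes early clearance less likely, but it is an accrual forecast and does not bind a cohort decision.

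Finally, one might infer that a level was in fact cleared wrongly. Section 7.3 records three patients at dose level 2 by October 2021, but the documents report no patient's DLT status or cycle 2 start. They show only that the rules permit it.

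**Conclusion.** The point stands as an inconsistency in the plan. The cycle 1 rules and the MTD definition treat a patient with a long toxicity delay of cycle 2 differently, and Section 14.1 does not settle which count applies. Read literally, such a patient is DLT-free for escalation and a DLT for the primary endpoint, and one such patient is enough to move a level from 1/6 to 2/6.

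The day count rests only on the 28-day cycle and the 21-day criterion. It applies to delays of cycle 2 and to holds that begin after day 8. The size does not follow from the documents: the gap in clearance probability, from about 8 percentage points (0.906 − 0.824) to about 26 (0.709 − 0.454), depends on assumed DLT rates and shows direction only. If delay DLTs are rarer than 5%, the gap is smaller. If escalation is already complete, the inconsistency still affects how DLTs are counted and how the MTD is reported.

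**What to change.** Reconcile the DLT window across the synopsis and Sections 1.2, 2.4.1, 7.2, 7.3, 14.1 and 14.3.2, so that the decision rules and the primary endpoint count the same events. State that a patient whose cycle 2 is pending is unresolved for the cohort decision until cycle 2 starts or the Table 9 delay criterion is met. For cohorts already decided, check whether any patient's cycle 2 was pending at the decision, and report the DLT count under the reconciled window.

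This is a wording change with no effect on the planned sample size range. Its cost is a wait of up to about 3 weeks before a cohort decision, and only when a patient's cycle 2 is delayed.
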